12.2.1 CAUSALITY (RELATIONSHIP TO MEDICAL DEVICE) ASSESSMENT

The investigator or physician sub-investigator must indicate whether he/she believes the AE is not related, unlikely related, possibly related (reasonable possibility that the medical device caused the AE), probably related, or definitely related to the medical device.

The Investigator should pay careful attention to the attribution of relation for all adverse events. Because there are many similar events between the TheraSphere and the sorafenib safety profile, judgment of relation by time of administration and patient assignment to treatment or control group should be considered.

An adverse event becomes an adverse device effect when the adverse event is considered associated with the use of the test device if the attribution is Possibly, Probably or Definitely Related. Relation to TheraSphere (screening, procedure, embolization or radiation) is not appropriate for the Control Group. Only those events with a possible, probable or definitely related attribution to TheraSphere will subject to expedited reporting. All other events documented in the trial will be addressed through periodic clinical trial reporting.

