For those patients without the pre-treatment high risk factors noted above, TheraSphere is very well tolerated, with treatment in the US commonly administered in an outpatient setting. Hospitalization for treatment effects associated with TheraSphere administration is rare. The most commonly reported adverse events associated with TheraSphere administration are fatigue, abdominal pain, nausea/vomiting and transient laboratory values including elevated bilirubin, AST, ALT, alkaline phosphatase, decreased platelets and lymphocyte depression with no clinical sequelae.

In this trial, all patients with unresectable HCC eligible for treatment with SOC sorafenib may be considered for study participation. Patients who meet the entry criteria will be randomized to either the patient's planned SOC sorafenib therapy (Control group), or to TheraSphere administered prior to the patient's SOC sorafenib therapy (Treatment group). The primary outcome measure for this trial is overall survival.

Our outcome assumption in the Control group is based on the SHARP trial, with a median overall survival of 10.7 months for patients treated with sorafenib. We assume a median overall survival of 14.2 months in the Treatment group, (hazard ratio = 0.754). However, due to uncertainty in the expected treatment effect, a sample size re-estimation is planned, which would allow the sample size to increase in order to detect a smaller increase in median OS time, from 10.7 months in the sorafenib arm to 13.7 months in the TheraSphere arm (ie, hazard ratio = 0.781).

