12.2 RECORDING ADVERSE EVENTS

All adverse events and adverse device effects will be documented from the date of randomization until study exit. For patients who permanently discontinue sorafenib in either arm of the study, AEs will be documented for 30 days from the date of discontinuation. After this period, only AEs considered to be related to TheraSphere will be collected.

In this study, patients should be encouraged to report adverse events spontaneously or in response to general, non-directed questions. At any time during the study, the patient may volunteer information that resembles an adverse event. Once it is determined that an adverse event has occurred, the Investigator should obtain all the information required to complete the adverse event form. Any medical management of an event and the date of resolution of the event must be recorded in the source document and on the appropriate case reports form(s) using medical terminology according to sponsor instructions.

For each AE, the following information will be recorded:

- Adverse event
- Serious/non-Serious
- Severity (Toxicity Grade)
- Action taken
- Relationship to study treatment
- Expected/Unexpected
- Date and time of onset
- Date and time of resolution

An expected adverse event is any AE, the nature or severity of which is identified in the relevant Package Insert.

Any AE experienced by a subject will be followed until the AE has resolved to the investigator's or physician sub-investigator's satisfaction. If a problem still exists, then the investigator or physician sub-investigator at his/her discretion will ask the subject to come back to the clinic for further evaluation. Any serious adverse events should be managed as discussed in Section 12.3.

Once the subject has been discharged from the study, the investigator has no obligation to seek further follow-up with the subject in order to identify new AEs. However, if the investigator becomes aware of an SAE that has occurred following the subject's discharge from the study and the investigator considers the SAE possibly, probably, or definitely related to a study drug or device, then the investigator should report the SAE as described in the protocol.

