5.2.5 Analysis Population

For the Per Protocol population, the protocol states that patients in this population will be analyzed according to the treatment actually received. Since patients who did not receive the treatment they were randomized to receive prior to progression by investigator assessment will be excluded from the Per Protocol population, the treatment actually received will be identical to the treatment randomized to receive. Hence, patients in this population will be analyzed according to the treatment group to which they were randomized.

For the safety analysis population, the protocol defines this population as all randomized patients who received at least one administration of study treatments and will be analyzed according to the treatment actually received. However, for patients with progression by investigator assessment, only study treatments received prior to progression will be used in the derivation of this population. Since both TheraSphere and sorafenib are allowed as best available care post progression, there are patients who received part of their randomized study treatment only after progression.

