6.5.2 Adverse Events

All adverse events (AEs) will be documented from the date of randomization until study exit. For patients who permanently discontinue sorafenib in either arm of the study, AEs will be documented for 30 days from the date of discontinuation. After this period, only AEs considered to be related to TheraSphere will be collected.

A treatment emergent AE (TEAE) is defined as an event that was not present at baseline or worsened in severity following the start of treatment through to 30 days after the end of the last study treatment (sorafenib and/or TheraSphere) initiated prior to progression

date by investigator assessment, or start date of subsequent HCC therapy, whichever comes first.

The start of treatment will be defined as the start date of sorafenib and the date of first angiogram, prior to progression date by investigator assessment, whichever occurs first. The last study treatment will be sorafenib for patients who received only sorafenib or both sorafenib and TheraSphere prior to progression, and will be TheraSphere for patients who only received TheraSphere prior to progression. Partial AE start and stop dates will be imputed as described in Section 6.2.1.3.

The investigator's verbatim term of an AE will be mapped to a system organ class and preferred term using the MedDRA Version 14.0 dictionary (Medical Dictionary for Regulatory Activities). The investigator will use the NCI Common Toxicity Criteria for Adverse Events [CTCAE] (version 4.0) or the protocol specific criteria when no NCI CTC criteria are available for the AE to determine the severity of the AE.

Adverse events related to sorafenib, device, and angiographic procedures are defined as those events recorded on the eCRF with relationship of possibly, probably, or definitely relationship. Relation to TheraSphere (device) is not appropriate for the Control group.

The incidence of TEAEs will be the number of patients who had the AE (counted only once) divided by the number of patients in the safety population and represented as a percentage. For subgroup summaries of AEs, the percentage will be represented as the number of patients with the AE event divided by the number of patients of that group in the safety population. The incidence of AEs will be the number of times an event occurs, counting worsening events only once. For worsening events, the AE end date of the earlier AE will be the same as the start date of the same AE with a higher severity.

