8.7.2 Adverse Events

The investigator's verbatim term of each AE will be mapped to system organ class and preferred term using the MedDRA Version 14.0 dictionary.

Adverse events will be summarized by system organ class and preferred term; a patient will only be counted once per system organ class and once per preferred term within a treatment. Patient counts and percentages and event counts will be presented for each treatment group for the following summaries:

1. Overall summary of TEAEs
2. All TEAEs (also presented by preferred term only in descending order).
3. All TEAEs with CTCAE grade ≥ 3 (also presented by preferred term only in descending order).
4. All TEAEs considered related to sorafenib.
5. All TEAEs considered related to device (ADE).
6. All CTCAE grade ≥ 3 TEAEs considered related to device.
7. All TEAEs related to angiographic procedure.
8. All TEAEs with fatal outcome.
9. All treatment emergent serious adverse events (SAE).
10. All treatment emergent serious adverse device events (SADE)
11. All TEAEs leading to sorafenib discontinuation
12. All TEAEs of special interest (presented by AESI category and preferred term)
13. All TEAEs of special interest with CTCAE grade ≥ 3 (presented by AESI category and preferred term)

Event rate (per 100 patient years) will also be presented by treatment group for each of the above TEAE categories. For each category, the event rate is defined as the number of patients with TEAEs in that category divided by the total duration of patients at risk for TEAEs and then multiplied by 365.25×100 to present in terms of per 100 patient years.

For the summary of TEAEs by CTCAE grade, if a patient has multiple events occurring in the same body system or same preferred term, then the event with the highest CTCAE grade will be counted. For TEAEs by relationship to study device, if a patient has multiple events occurring in the same body system or same preferred term, the event with the highest association to study device will be summarized (unknown is considered a higher association to study device than not related, but less of a relationship than possibly, probably, and definitely). Adverse events related to sorafenib, device and angiographic procedure are defined as a subset of AEs with a relationship of either possibly, probably, definitely, or unknown.

No statistical inference between the treatments will be performed on AEs.

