11.4 APPENDIX 4: Definition and Derivation of Subsequent HCC Therapy

A patient is considered to have received ‘subsequent HCC therapy’, after the protocol required treatments, if they had

- a subsequent systemic anti-cancer treatment (excluding sorafenib), and/or
- a non-protocol liver directed therapy (excluding ablation/surgery)

Subsequent systemic anti-cancer treatment will be identified using all non-sorafenib records from the “Best Available Care - Post Treatment Discontinuation – Medication” eCRF page. Note that all records on the “Best Available Care - Post Treatment Discontinuation – Medication” eCRF page are expected to be systemic anti-cancer treatments for HCC after data cleaning has been completed.

Non-protocol liver directed therapy will be identified using all records (except ablation/surgery) from “Additional Procedures” eCRF page. This eCRF page captures any procedures relating to liver directed therapies outside the study protocol, such as liver ablation, liver surgery, liver external beam radiation therapy, SIRT with rhenium, SIRT with Y90 (including TheraSphere for patients randomized to control group), TACE, and transarterial embolization (TAE). The free text field “procedure term” will be reviewed and categorized by physician, which will be finalized prior to the database hard lock. Procedures identified as liver ablation and liver surgery by physician’s review will not be considered as subsequent HCC therapy.

Notes:

- Treatments recorded on the “Resection / HCC Stage Migration” eCRF page will not be considered as subsequent HCC therapy, since these treatments are delivered to patients who had a downstaging of disease and represents a population possible to have better outcomes and important to follow-up.
- TheraSphere treatment/retreatment for patients randomized to TheraSphere group, recorded on the “TheraSphere Doses Administered” eCRF page, are study treatment per protocol, so will not be considered as subsequent HCC therapy.

[figure not shown]
**11.5 APPENDIX 5: Statistical Details of the Adaptive Design for Protocol TS-103
STOP-HCC**

Statistical Details of the Adaptive Design

1 Design Overview

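### Device attribution is ruled out by randomized arm, so a serious, labelled TheraSphere effect in a control patient who receives the device has no 24-hour report and, late on, is not collected

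*Protocol*

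**What the plan says.** **The attribution rule.** Protocol 12.2.1: "Relation to TheraSphere (screening, procedure, embolization or radiation) is not appropriate for the Control Group". SAP 6.5.2: "Relation to TheraSphere (device) is not appropriate for the Control group". The Control group is the randomized arm; Protocol 5.3 describes eligible patients as "randomized to either the patient's planned SOC sorafenib therapy (Control group" or to TheraSphere before sorafenib. Protocol 12.2.1 also requires the investigator to rate each AE's relation to the device on a five-level scale, and says that "judgment of relation by time of administration and patient assignment to treatment or control group should be considered".

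**What depends on it.** Protocol 12.2.1 limits expedited reporting to events rated at least possibly related to TheraSphere and leaves the rest to periodic reporting. Protocol 12.3 sets a 24-hour report to the sponsor for SADEs and UADEs. Protocol 12.2 records all AEs in both arms until 30 days after permanent sorafenib discontinuation, and then: "After this period, only AEs considered to be related to TheraSphere will be collected". SAP 6.5.2.2 and 6.5.2.3 define ADEs and SADEs by the recorded relation to the device.

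**Device use in control patients.** SAP 8.3.3 excludes from the Per Protocol population any control patient given Y90, TheraSphere included, before progression. SAP Appendix 4 names, among the procedures captured on the Additional Procedures eCRF page, "SIRT with Y90 (including TheraSphere for patients randomized to control group".

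**The concern.** The attribution rule follows assignment, while the risk of a device effect follows exposure. The two agree only if no control patient ever receives TheraSphere, and the SAP provides for control patients who do. In such a patient the same event after the same device would be handled differently from one in the Treatment group, purely because of the arm. At stake is device-safety capture: whether a serious device effect reaches the sponsor within 24 hours, whether it is collected at all late in follow-up, and whether it is ever called an ADE or SADE.

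**Working it through.** The documents give no figure to reproduce. The check traces one event, judged by the investigator to be a TheraSphere effect, through each rule.

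| Rule | Where | Control patient given TheraSphere | Treatment-group patient |
|---|---|---|---|
| Relation to device | Protocol 12.2.1; SAP 6.5.2 | Ruled out | Rated |
| ADE/SADE status | SAP 6.5.2.2, 6.5.2.3 | None, for want of a device relation | Yes, if at least possibly related |
| 24-hour SADE report to sponsor | Protocol 12.2.1, 12.3 | Closed | Open |
| Prompt IRB notice of unexpected SAEs | Protocol 12.3 | Open | Open |
| Recording until 30 days after permanent sorafenib stop | Protocol 12.2 | Yes, without device relation | Yes, with device relation |
| Collection after those 30 days | Protocol 12.2 | Closed | Open |
| SAE learned of after discharge | Protocol 12.2 | Reportable if related to a study drug or device | Same |
| TEAE tables | SAP 5.2.6, 6.5.2, Appendix 4 | Window closes, at the latest, when TheraSphere starts | TheraSphere is study treatment and does not close the window |

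**Which events fall through.** Protocol 12.2 calls an event expected if its nature or severity is in the relevant package insert. A serious, labelled TheraSphere effect is therefore not an unexpected SAE, so the prompt IRB notice does not cover it. It is not a UADE either, because that term is reserved for effects not already identified. The only 24-hour route left is the SADE route, and the attribution rule closes it.

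**The late period.** A control patient who stops sorafenib for good and later receives TheraSphere can have a device effect more than 30 days after the last sorafenib dose. Only TheraSphere-related AEs are then collected, and relation to TheraSphere is ruled out for this arm. The discharge clause in the same section has no arm limit. The result is inconsistent: an SAE related to the device is reportable once the patient has left the study, but not collectable while the patient is still followed.

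**The tables.** SAP 8.7.2 summarizes "All TEAEs considered related to device (ADE"), so only treatment-emergent events count. Appendix 4 makes TheraSphere in a control patient a subsequent HCC therapy, and SAP 5.2.6 and 6.5.2 end the TEAE window at its start date at the latest. Allowing attribution would leave these tables essentially unchanged.

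**The safety grouping.** SAP 8.3.2 groups patients by treatment received before investigator-assessed progression. A clash between as-treated grouping and arm-based attribution can therefore arise only for use before progression. Even then the placement is unsettled, because Appendix 4 treats this use as outside the protocol and SAP 6.5.1.1 presents TheraSphere exposure for the Treatment arm only.

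**Scale.** The documents do not say how many control patients received TheraSphere. With 520 patients randomized 1:1, the control arm has about 520 / 2 = 260. If the share were 5% (an assumption), that would be 260 × 0.05 = 13 patients; at an assumed 20%, 260 × 0.20 = 52.

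**The case against.** The strongest reply is that the gap is narrow and the other rules catch most of what matters. Protocol 12.2.1 tells the investigator to rate device relation and makes arm a factor to weigh. All AEs in both arms are recorded for a defined period. Unexpected SAEs go promptly to the IRB, and the discharge clause has no arm limit. SAP 8.7.2 even counts an unknown device relation as related. All of this is correct, and a reader who inferred that such an event can never be reported, or that every safeguard fails at once, would go beyond the text. What remains is the serious, labelled effect and the late period, which none of these provisions covers. The general instruction to rate relation does not rescue them, because the sentence specific to the Control Group removes it.

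A second reply is that crossover is barely foreseen. SAP 5.2.5 does say "Since both TheraSphere and sorafenib are allowed as best available care post progression", but the rest of that sentence concerns patients who got part of their randomized treatment only after progression, which fits the Treatment group; it is weak evidence of control use. Protocol 15.0 also lists liver-directed therapy outside the protocol after intra-hepatic progression as a major deviation. Both points are fair. SAP 8.3.3 and Appendix 4 still name the case directly, and a safety rule has to work for deviations too.

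A reader might also infer that device-related counts in the AE tables are biased low because of the attribution rule. The documents do not support that: the TEAE cut-off removes these events whatever their attribution. Nor do they show that the eCRF blocks the field, since no case report form is supplied.

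**Conclusion.** The concern holds as a gap in safety reporting and collection. Read literally, Protocol 12.2.1 and SAP 6.5.2 deny a device relation to any control patient, including one treated with the device. A serious, labelled device effect in that patient then has no 24-hour route to the sponsor and no SADE status, and more than 30 days after permanent sorafenib discontinuation it is not collected during follow-up.

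The size is unknown. The 13 to 52 patients above only show scale under an assumed 5% to 20% share. It is tempting to multiply them by the 19% grade 3/4 bilirubin toxicity that Protocol 5.3 quotes from a single-centre cohort, but that would not estimate missed SADEs: toxicity grade is not the SAE definition in Protocol 12.1.1. The conclusion rests on two readings: that Control Group means the randomized arm, and that the sentence is applied as written. Sample size, power and alpha are unaffected. The change should be made; it is cheap and concerns device safety, though probably in few patients.

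**What to change.** 1. In Protocol 12.2.1 and SAP 6.5.2, replace the arm-based sentence with an exposure-based one: relation to TheraSphere is recorded for any patient, in either arm, who has had a TheraSphere work-up or administration, and is not applicable only where neither has taken place.
2. State in Protocol 12.2 and 12.3 that the late-collection and expedited-reporting rules apply to these patients.
3. Reconcile Protocol 12.2, 12.2.1 and 12.3 with SAP 6.5.2, 8.3.2 and Appendix 4, including which safety group holds a control patient given TheraSphere before progression.
4. Identify control recipients from the Additional Procedures page, review their recorded AEs for device relation, and list their ADEs and SADEs separately, outside the TEAE window. An extra line within the SAP 8.7.2 tables would be essentially empty.

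The cost is a little added site reporting and medical review. Timing limits the benefit: SAP 5.2.1 says all 520 patients were randomized before the first interim analysis, and SAP version 6.0 (15 September 2022) postdates the latest planned final-analysis date of 30 April 2022. Step 4 is therefore the part most clearly still open, and late events that were never collected may not be recoverable. The report should say so.

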12.3 SUBMITTING EXPEDITED SAFETY REPORTS

Any SADE or UADE (defined previously) must be reported by telephone or fax to the sponsor or designate as specified in the study procedures within 24 hours of learning of the event. In the event of an emergency, the Investigator will contact the CRO using the coordinates specified in the study procedures.

The SAE form provided by the sponsor should be completed and signed by the investigator or physician sub-investigator. The entire SAE form needs to be completed, if possible, to keep requests for additional information to a minimum. **Patients experiencing SAE, SADE or UADE should be followed clinically and with laboratory studies, if appropriate, until medical treatment and/or medical monitoring of the event is no longer required because the event resolves or stabilizes, returns to baseline if a baseline value is available, can be attributed to agents other than the study treatments or a referral for appropriate follow-up care has been made.**

The Investigator must promptly inform the IRB of all unexpected SAE or UADE. These events will be reported by the sponsor or its designate as appropriate to the regulatory authorities according to relevant jurisdictional medical device regulations. The Investigator will receive notification of these events across all study centers from the sponsor.

Each AE reported on an SAE form must also be reported in the adverse event section of the eCRF.

